4.3. Prior and Concomitant Medications

All medications (including statin, non-statin LMT, and CV) taken from the time of informed consent to the final study visit, including medications that were started before the study and are ongoing during the study, will be reported in Concomitant Medications CRF.

All medications will be dictionary coded using the World Health Organization-Drug Dictionary (WHO-DD) to both an anatomic category and a therapeutic category, with the version in effect at the time of the first database lock. Drug names will be matched to respective Anatomical-Therapeutic-Chemical (ATC) classification, although a drug can be matched to more than one ATC classification (i.e. patients can be counted in several categories for the same medication).

Prior medications, concomitant medications, and post-treatment medications are defined below and will be applied in the respective treatment periods (DBTP and OLTP for Group B only).

- Prior medications are defined as medications for which the stop date is before the date of the first DBTP study treatment administration.
- Concomitant medications are defined as medications that are administered to the patients during the respective study treatment periods. Specifically:
 - Start date of the concomitant medication is on or after the first study treatment administration in respective study treatment periods (\geq DBTP Day 1 or \geq OLTP Week 24 for Group B only); **or**
 - Start date of the concomitant medication is before the first study treatment administration in respective study treatment periods and is “Ongoing” during the treatment emergent period; **or**
 - Start date of the concomitant medication is before the first study treatment administration in respective study treatment periods, and the end date is on or after the first study treatment administration in respective study treatment periods (\geq DBTP Day 1 or \geq OLTP Week 24 for Group B only).

The concomitant medication treatment emergent periods are defined as:

- For concomitant medications in the DBTP, the treatment emergent period is defined from the first day of double-blind study treatment administration to the last day of double-blind study treatment +168 days (for Group A patients or Group B patients who do not continue into the OLTP) or to the day before the first open-label study treatment administration (for Group B patients who enter the OLTP).
- For concomitant medications in the OLTP (Group B only), the treatment emergent period is defined from the first day of open-label study treatment administration to the last day of open-label study treatment +168 days.

Note: In the case the start date is before first study treatment administration and both ongoing status and stop date are missing, the medication will be assumed to be concomitant.

- Post-treatment medications are defined as medications for which the start date is after last date of study treatment administration +169 days (\geq last study treatment +169 days).

4.4. Prohibited Medications and Procedures During Study

The definitions of prohibited medications and procedures are described in the section 7.8.1 of the protocol. They will be reviewed and identified by the study clinician and reported in protocol deviations.

4.5. Patient Disposition

Patient disposition will include the description of patient status at major milestone decisions in the study, as well as the patient analysis populations.

For patient study status, patient milestone categories for the DBTP are defined below. As applicable, percentages will be calculated using the number of randomized patients in the denominator, with two exceptions. Specifically, the two exceptions will be for the screened and non-randomized categories, which will not have associated percentages shown.

- The total number of screened patients, defined as originally having met the inclusion criteria and signed the ICF.
- The total number of screen failure (SF) patients:
 - if a SF patient’s first informed consent date is before randomization date of the last IV patient, this patient will be included in Group B; otherwise this patient will be included in Group A
- The total number of randomized patients, defined as all screened patients with a double-blind treatment kit number allocated and recorded in the IVRS database, regardless of whether the treatment kit was used.
- The total number of patients randomized but not receiving study treatment.
- The total number of patients randomized and receiving study treatment.
- The total number of patients who completed the DBTP as collected on the end of double-blind treatment e-CRF.
- The total number of patients who completed the DBTP, defined for Group A as at least 15 weeks of study treatment administration and week 16 visit performed; and defined for Group B as at least 20 weeks of study treatment administration and week 24 visit performed
- The total number of Group B patients who completed week 16 visit, defined as at least 12 weeks of study treatment administration and week 16 visit performed
- The total number of patients who prematurely discontinued study treatment during the double-blind period, and the reasons for discontinuation collected on the End of Double-blind Treatment e-CRF
- The total number of patients in Group B who do not proceed into OLTP and complete the last study follow-up visit (i.e. Follow-up week 20).
- The total number of patients in Group A who complete the last study follow-up visit (i.e. Follow-up week 20).
- The total number of patients who did not complete the study follow-up period, defined as the last visit performed less than 23 weeks after the last study treatment administration. Patients who died during the study are excluded. (For Group B this applies only to patients who did not proceed to OLTP).

Patient milestone categories for the OLTP (Group B only) are defined below. As applicable, percentages will be calculated using a denominator of the number of patients administer open-label study treatment.

- The total number of patients receiving open-label study treatment.

- The total number of patients ongoing in OLTP (applicable for the first step analysis)
- The total number of patients who completed the OLTP as collected on the end of open-label treatment e-CRF.
- The total number of patients who completed the open-label treatment period, defined as at least 44 weeks of open-label study treatment administration and visit week 72 performed.
- The total number of patients who prematurely discontinued study treatment during the OLTP, and the reasons for discontinuation collected on the End of Open-label Treatment e-CRF.
- The total number of patients from OLTP who complete the last study follow-up visit (i.e. Follow-up week 20).
- The total number of patients who did not complete the study follow-up period, defined as the last visit performed less than 23 weeks after the last study treatment administration. Patients who died during the study are excluded

The following patient populations for analyses are defined below:

- Randomized population
- Efficacy populations: ITT and mITT populations
- Double-blind safety analysis set
- Open-label safety analysis set
- Anti-evincumab antibody (ADA) analysis set
- Pharmacokinetic (PK) analysis set
- Pharmacodynamic (PD) analysis set

The following patient listings will provide the details from the patient disposition table.

- A listing of patients treated but not randomized, patients randomized but not treated, and patients randomized but not treated as randomized.
- A listing of patients prematurely discontinued from treatment, along with reasons for discontinuation.

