Randomization will be stratified by high-intensity statin (Yes/No) and HeFH (Yes/No) at baseline. High-intensity statin is defined as rosuvastatin 20 mg or 40 mg daily, atorvastatin 40 mg or 80 mg daily, or simvastatin 80 mg daily (if already on this dose for >1 year). To ensure an adequate number of patients with HeFH are included in this study and exposed to each dose, randomization will be stratified 2:1 (HeFH:non-HeFH; 24:12) within each treatment group.

Investigational medicinal product (IMP) administration during the double-blind treatment period will take place at the site and possibly, by visiting home nurses (only for the SC group). The IMP will be administered at the site on the day of randomization, after all samples for clinical laboratory evaluation have been obtained. In order to ease burden for those patients randomized to receive SC IMP, visiting home nurses may be utilized to administer SC IMP on odd visit dates, eg. Week 1, week 3, and week 5.

Open-Label Treatment Period (Group B only)

Patients in Group B (the IV treatment groups) will enter a 48-week open-label treatment period and all patients will receive evinacumab 15 mg/kg IV Q4W.

Follow-Up Period (Groups A and B)

All patients will be followed for 24 weeks after the last dose of study drug.

Patients should maintain their stable background LMT regimen from screening through the end of study (EOS) visit.

Patients will be reminded to adhere to a heart-healthy diet at screening, and continuing through the EOS visit. Patients should maintain a stable exercise level for the duration of the study, and avoid rigorous exercise 24 hours before each study visit. All lipid results will be blinded from after randomization until the week 36 visit for the IV cohorts, and until database lock for the SC cohorts.

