5.1.2. Follow-up

All patients will be followed for 24 weeks after the last dose of study drug. Thus, for IV cohorts in which the dosing interval is Q4W, patients will be followed for an additional 20 weeks after end of treatment (EOT). For SC cohorts, in which the shortest dosing interval is QW, patients will be followed for an additional 23 weeks after the EOT visit. Patients in Group B may have the option of joining an open-label extension or safety study after successfully completing the treatment period (48 weeks). Patients in Group A may have the option of joining an open-label extension or safety study after successfully completing the treatment period (16 weeks) and follow-up period (24 weeks). Those patients that do not enroll in the separate open-label study will enter a follow-up period, which lasts 20 weeks for IV groups after the last dose of study drug. It takes approximately 24 weeks for evinacumab concentration to be below lower limit of quantitation.

Sexually active patients should be reminded at the EOT visit to maintain highly effective contraceptive measures for 24 weeks after the last dose of study drug. At this visit, women of childbearing potential (WOCBP) may be provided urine pregnancy tests to perform at home with instructions to test for pregnancy 4 weeks after this visit and Q4W thereafter. The patient should also be notified of Q4W follow-up phone calls to confirm contraception use, provide a reminder of pregnancy reporting, and to obtain the results of the pregnancy test.

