10.4.1. Patient Disposition

The following data will be summarized:

- The total number of screened patients, defined as having met the inclusion criteria and signed the ICF.
- The total number of randomized patients, defined as all screened patients with a double-blind treatment kit number allocated and recorded in the IVRS database, regardless of whether the treatment kit was used.

For any patient randomized more than once, safety data from the first randomization will be included in the SAF, with safety data associated with the later randomization reported separately. Since this is expected to be a rare event, inclusion of efficacy data from the patient randomized more than once in the efficacy population will be decided on a case-by-case basis prior to the unblinding of treatment assignments and will be documented in the clinical study report.

- The total number of patients randomized, but not receiving study treatment
- The total number of patients randomized and receiving study treatment
- The total number of patients who completed the double-blind treatment period, defined for Group A as at least 15 weeks of study treatment exposure and week 16 visit performed; and defined for Group B as at least 20 weeks of study treatment exposure and week 24 visit performed
- The total number of Group B patients who completed week 16 visit, defined as at least 12 weeks of study treatment exposure and week 16 visit performed
- The total number of Group B patients who completed the open-label treatment period, defined as at least 44 weeks of open-label study treatment exposure and visit week 72 performed.
- The total number of patients who prematurely discontinued study treatment during the double-blind treatment period, and the reasons for discontinuation
- The total number of patients who prematurely discontinued study treatment during the open-label treatment period, and the reasons for discontinuation
- The total number of patients who did not complete the study follow-up period, defined as the last visit performed less than 23 weeks after the last study treatment administration. Patients who died during the study are excluded
- The total number of patients in each analysis set
- A listing of patients treated but not randomized, patients randomized but not treated, and patients randomized but not treated as randomized
- A listing of patients prematurely discontinued from treatment, along with reasons for discontinuation

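### The open-label follow-up non-completion count has no exclusion for Group B patients who enter the extension study, and the Group A completion item names Follow-up week 20 where the schedule ends at week 23

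*SAP*

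**What the plan says.** **Non-completion rule.** SAP 4.5 lists the item twice, once for the double-blind period and once for the open-label period: "The total number of patients who did not complete the study follow-up period, defined as the last visit performed less than 23 weeks", with the interval counted from the final dose. Both add "Patients who died during the study are excluded". The double-blind item then adds "For Group B this applies only to patients who did not proceed to OLTP". The open-label item has no second exclusion. Protocol 10.4.1 states the rule once, excluding deaths only.

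**Who enters Group B follow-up.** Protocol 5.1.2: "Those patients that do not enroll in the separate open-label study will enter a follow-up period, which lasts 20 weeks for IV groups". The synopsis and Protocol 5.1 agree on timing. Group B patients may be offered the extension once the double-blind and open-label periods are complete, whereas under Protocol 5.1 Group A patients must also finish follow-up. Against this, Protocol 5.1 also says "All patients will be followed for 24 weeks after the last dose of study drug", Protocol 3.2.1 says much the same, and Protocol 5.1.2 itself opens with that statement.

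**Open-label completion.** Protocol 10.4.1: "defined as at least 44 weeks of open-label study treatment exposure and visit week 72 performed".

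**Group A completion.** SAP 4.5: "The total number of patients in Group A who complete the last study follow-up visit (i.e. Follow-up week 20"). The preceding item for Group B uses the same week. Protocol 5.1.2, the flow diagram (SAP 2.3) and SAP Appendix 10.2 Table 3 all place the end of Group A follow-up 23 weeks after the end-of-treatment visit.

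**The concern.** The SAP recognises that moving on to the next treatment phase differs from being lost, and excludes such patients from the double-blind count. The same situation arises at the end of open label, where patients may move to an extension, and there the exclusion is missing. No row in the list shows extension entry either. Planned rollover and loss to follow-up after week 72 therefore fall into one number.

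This matters because the treatment-emergent period runs to 168 days after the last dose on the ground of residual drug effect (Protocol 10.4.4.1, SAP 4.8.1). The disposition table is where a reader learns how much of that window was observed. SAP 5.8.1 also gives event-free open-label patients exposure time equal to the treatment-emergent period, so a reader of those rates needs to know how many patients left this study soon after the last infusion.

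The Group A item is a second fault in the same list: it identifies completion of follow-up by a contact that is not the last one.

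**Working it through.** **Inputs.** Group B: last open-label infusion Day 477 (week 68) and end of open label Day 505 (week 72), Table 5; end of study Day 645, Table 7. Group A: last dose week 15 (Protocol 7.6), which is Day 106; end of treatment Day 113, Table 3; phone Visit 23 on Day 253 and end of study Day 274, Table 6. Formula: weeks = (later day − earlier day) / 7.

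**Reproducing the plan's follow-up lengths.**
- Group B: (645 − 505)/7 = 20.0 weeks after end of treatment; (645 − 477)/7 = 24.0 weeks after the last dose.
- Group A: (274 − 113)/7 = 23.0 weeks after end of treatment; (274 − 106)/7 = 24.0 weeks after the last dose.

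These match Protocol 5.1.2 and the flow diagram.

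**Group B patient entering the extension at week 72, tested against the 23-week threshold.**

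| Case | Calculation | Weeks after last dose |
|---|---|---|
| On schedule | (505 − 477)/7 | 4.0 |
| Dose 3 days early, visit 3 days late | (508 − 474)/7 | 4.9 |
| Dose 14 days early (Protocol 7.1 window), visit 3 days late | (508 − 463)/7 | 6.4 |
| Week-68 dose skipped | (505 − 449)/7 | 8.0 |

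All are well below 23, so each such patient is flagged.

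**How many.** The documents give no rollover rate. Assume, as a ceiling, that all 108 randomized Group B patients enter and complete open label. Rollover of 25, 50, 75 or 100% then puts 27, 54, 81 or 108 patients in the non-completion count. Dropout lowers these figures. SAP 4.5 bases open-label percentages on patients given open-label drug, not on the 108 randomized.

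**Group A item.** In SAP Appendix 10.2 Table 1, FU-W20 for Group B completers is Day 645, which is 140 days after Day 505, so the label counts from end of treatment. For Group A, 20 weeks after end of treatment is 113 + 140 = Day 253, phone Visit 23. That is (253 − 106)/7 = 21.0 weeks after the last dose, and at most (260 − 103)/7 = 22.4 with the dose 3 days early and the call 7 days late. Both are below 23. A Group A patient last contacted then satisfies the completion item as labelled and also meets the definition of not completing. Group A's follow-up windows in Appendix 10.2 Table 3 are FU-W8, FU-W16 and FU-W23; there is no FU-W20.

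**The case against.** **The count is literally true.** A patient who leaves this study about 4 weeks after the last dose did not have the 24-week post-dose window observed here, and simply dropping such patients would make follow-up look more complete than it was. This stands, and it shapes the fix: rollover must stay visible. It does not rescue the present rule, which gives one number for two different things.

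**The protocol also says everyone is followed for 24 weeks.** On that reading a rollover patient would have later visits and would not be flagged. Protocol 5.1.2 is more specific, and the extension timing in the synopsis and Protocol 5.1 supports it, but the contradiction is real and belongs in the fix.

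**Other rows limit the damage.** Open-label completers, early discontinuations with reasons, and completers of the last follow-up visit are also reported. That is correct. What stays mixed is rollover and losses after week 72 among patients who should have entered follow-up.

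**The Group A label looks like a copying slip.** Read by its main words, completion of the last follow-up visit, the item would still count Day 274 completers. A reader might infer that Group A has no week-20 contact, so that its completer count would be zero or undefined, with up to 144 patients uncounted. The documents do not support that. Table 6 has Group A phone contacts at study week 20 (Day 141) and at 20 weeks after end of treatment (Day 253), and the analysis windows assign measurements to time points rather than define disposition. The supported statement is that the item names the wrong visit.

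**Conclusion.** Both faults hold. The open-label item in SAP 4.5 and the rule in Protocol 10.4.1 classify every Group B patient who goes straight into the extension after week 72 as not completing follow-up, with a gap of 4.0 weeks on schedule and at most 8.0 weeks in the cases tested, against a threshold of 23. This assumes that Protocol 5.1.2 governs who enters follow-up. The Group A completion item carries the Group B week and can contradict the non-completion item for the same patient.

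The size is 0 to all open-label completers. Entry to the extension is only a possibility, and any specific percentage is an assumption. A reader might also take the deaths-only exclusion to apply throughout; it does not, because the double-blind item already leaves out Group B patients who went on to open label. Nor does the point reach the trial's inference: it concerns descriptive disposition and safety-completeness counts, and no efficacy estimate, alpha or power figure changes.

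**What to change.** 1. In the SAP 4.5 open-label list and in Protocol 10.4.1, add a disposition row for patients who entered the extension or safety study at the end of the open-label period.
2. Limit the open-label non-completion count, and the Group B part of the Protocol 10.4.1 count, to patients who did not enter the extension, mirroring the parenthesis in the double-blind item. Show the rollover row beside it, with a note that this study's post-dose window was not fully observed for those patients. State the denominator of each row.
3. Change the Group A completion item to Follow-up week 23 (Day 274), to agree with Table 6 and Appendix 10.2 Table 3.
4. Reconcile the statements in Protocol 3.2.1, 5.1 and the opening of 5.1.2 that all patients are followed for 24 weeks with the later sentence in 5.1.2 that limits Group B follow-up to patients not joining the separate study.
5. SAP 7.4 mentions insufficient follow-up at the first two analysis steps without defining it. If the same rule is meant, say so and apply the same wording.

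The cost is SAP and protocol wording, plus confirmation that extension entry is recorded for each patient. No visit, sample or analysis model changes.

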4.6. Study Treatment Exposure and Compliance Variables

Study treatment exposure variables for injections administered during the DBTP for Group A patients are listed below with associated definitions:

- Patient duration of double-blind study treatment exposure in weeks defined as: $(\text{last study drug dosing date} + 7 - \text{first study drug dosing date} + 1 \text{ day}) / 7$. Unplanned intermittent discontinuations in study treatment will be addressed on a case-by-case basis, since this is expected to be a rare occurrence.
- The total number of injections by patient

- The following categories will be used for treatment exposure at 1 week intervals: ≥ 1 day and < 1 week, ≥ 1 weeks and < 2 weeks, ≥ 2 weeks and < 3 weeks, ≥ 3 weeks and < 4 weeks, ≥ 4 weeks and < 5 weeks, ≥ 5 weeks and < 6 weeks, ≥ 6 weeks and < 7 weeks, ≥ 7 weeks and < 8 weeks, ≥ 8 weeks and < 9 weeks, ≥ 9 weeks and < 10 weeks, ≥ 10 weeks and < 11 weeks, ≥ 11 weeks and < 12 weeks, ≥ 12 weeks and < 13 weeks, ≥ 13 weeks and < 14 weeks, ≥ 14 weeks and < 15 weeks, ≥ 15 weeks and < 16 weeks, ≥ 16 weeks.

Study treatment exposure variables for infusions administered during the DBTP for Group B patients are listed below with associated definitions:

- Patient duration of double-blind study treatment exposure in weeks defined as: (last double-blind study treatment administration date +28 – first double-blind study treatment administration date + 1)/7. Unplanned intermittent discontinuations in study treatment will be addressed on a case-by-case basis, since this is expected to be a rare occurrence. Values will be rounded to one decimal place.
- The total number of double-blind study treatment infusions by patient.
- The following categories will be used for treatment exposure at 4 week intervals: ≥ 1 day and < 4 weeks, ≥ 4 weeks and < 8 weeks, ≥ 8 weeks and < 12 weeks, ≥ 12 weeks and < 16 weeks, ≥ 16 weeks and < 20 weeks, ≥ 20 weeks and < 24 weeks, ≥ 24 weeks.

Study treatment exposure variables for infusions administered during the OLTP for Group B patients are listed below with associated definitions:

- Patient duration of open-label study treatment exposure in weeks defined as: (last open-label evinacumab treatment administration date +28 – first open-label evinacumab treatment administration date)/7. Unplanned intermittent discontinuations in study treatment will be addressed on a case-by-case basis, since this is expected to be a rare occurrence. Values will be rounded to one decimal place.
- Patient duration of open-label study treatment exposure in patient-years defined as: (last open-label evinacumab treatment administration date +28 – first open-label evinacumab treatment administration date)/365, regardless of unplanned intermittent discontinuations.
- The total number of open-label evinacumab treatment infusions by patient.
- The following categories will be used for treatment exposure at 4 week intervals: ≥ 1 day and < 4 weeks, ≥ 4 weeks and < 8 weeks, ≥ 8 weeks and < 12 weeks, ≥ 12 weeks and < 16 weeks, ≥ 16 weeks and < 20 weeks, ≥ 20 weeks and < 24 weeks, ≥ 24 weeks and < 28 weeks, ≥ 28 weeks and < 32 weeks, ≥ 32 weeks and < 36 weeks, ≥ 36 weeks and < 40 weeks, ≥ 40 weeks and < 44 weeks, ≥ 44 weeks and < 48 weeks, ≥ 48 weeks

Study treatment exposure variables combining DBTP and OLTP are listed below for all Group B patients who received evinacumab in the DBTP:

- Cumulative patient duration of evinacumab exposure in weeks defined as: double-blind treatment exposure plus open-label treatment exposure, regardless of unplanned intermittent discontinuations.

- Cumulative patient duration of evinacumab exposure in patient-years defined as: double-blind treatment exposure in patient-years plus open-label treatment exposure in patient-years, regardless of unplanned intermittent discontinuations.
- Cumulative total number of evinacumab treatment infusions by patient defined as: total number of double-blind infusions plus total number of open-label infusions.
- The following categories will be used for cumulative patient treatment exposure at 4 week intervals: ≥ 1 day and < 4 weeks, ≥ 4 weeks and < 8 weeks, ≥ 8 weeks and < 12 weeks, ≥ 12 weeks and < 16 weeks, ≥ 16 weeks and < 20 weeks, ≥ 20 weeks and < 24 weeks, ≥ 24 weeks and < 28 weeks, ≥ 28 weeks and < 32 weeks, ≥ 32 weeks and < 36 weeks, ≥ 36 weeks and < 40 weeks, ≥ 40 weeks and < 44 weeks, ≥ 44 weeks and < 48 weeks, ≥ 48 weeks and < 52 weeks, ≥ 52 weeks and < 56 weeks, ≥ 56 weeks and < 60 weeks, ≥ 60 weeks and < 64 weeks, ≥ 64 weeks and < 68 weeks, ≥ 68 weeks and < 72 weeks, ≥ 72 weeks, etc.

With respect to patient treatment administration compliance, the study treatment is administered during the investigative site visits and therefore study compliance will be assessed by infusion/injection frequency for respective treatment periods, specifically:

- DBTP: The mean infusion/injection frequency for study treatment will be defined for each patient as the average number of days between 2 consecutive infusions/injections: $(\text{last double-blind dose date} - \text{first double-blind dose date}) / (\text{number of infusions/injections in DBTP} - 1)$, for patients receiving at least 2 infusions/injections.
- OLTP (Group B only): for each patient as the average number of days between 2 infusions: $(\text{last open-label dose date} - \text{first open-label dose date}) / (\text{number of infusions in OLTP} - 1)$, for patients receiving at least 2 infusions.

All important and minor protocol deviations potentially impacting efficacy analyses, randomization and drug-dispensing irregularities, as well as other deviations, will be collected and reviewed on an ongoing basis throughout the study as described in the Protocol Deviation Plan (PDP). Both monitoring collected and programmatically derived deviations are listed and defined in the PDP.

